7.1. Treatments Administered

Study Treatment	Hydroxychloroquine sulfate	Ascorbic acid	Lopinavir-ritonavir	Ascorbic acid	Azithromycin	Folic acid	Ondansetron	Loperamide
Dosage Formulation	200 mg (155 mg base) tablets	250 mg tablets	200 mg-50 mg tablets	250 mg tablets	250 mg tablets	400 µg tablets	4 mg tab	2 mg tab
Route of Administration		Oral						
Dosing Instructions	Take 2 tablets twice on Day 1 and 1 tablet twice a day for the subsequent 9 days, for a total of 10 days of treatment. Take at approximately the same time of the day with a meal or a glass of milk.	Take 4 tablets every 12 hours on Day 1, and 2 tablets twice daily for the 9 subsequent days, for a total of 10 days of treatment. Take at approximately the same time each day with a meal.		Take 2 tablets once on Day 1 and 1 tablet once a day for the subsequent 4 days, for a total of 5 days of treatment. Tablets can be taken with or without food.		Take 1 tablet as needed for nausea every 8 hours. Do not exceed 8 pills per 24 hour period.		Take 2 tablets as needed for diarrhea. Take 1 additional pill with each episode of diarrhea. Do not exceed 4 pills per 24 hour period.
	If a dose is missed, it should be taken as soon as possible. If it is less than 4 hours before the next dose, the dose should be skipped.							
Packaging and Labeling	The medication for home delivery will be dispensed in an otherwise-unmarked container with the study label. The container will be labeled with a unique identifier. The container will be packed in a standard box used for mail delivery of medications as needed.							
Manufacturer	Sandoz	Cardinal Health	Abbvie		Greenstone LLC NDC 59762-2198-3 (blister pack) NDC 59762-2198-3 (bottle)	Leader (distributed by Cardinal Health)	TBD	TBD

7.2. *Risks to the Participants*

7.2.1. *Risks Associated Administration with HCQ*

With tens of millions of doses of HCQ administered for malaria and autoimmune diseases, the side effect profile of HCQ is well described and the drug is generally well tolerated. With short-term administration (as opposed to chronic/year-long use in rheumatologic disease management), the major AEs are gastrointestinal (nausea, vomiting, dyspepsia, abdominal cramps, and diarrhea) and transient skin rashes. The gastrointestinal symptoms may vary by specific generic manufacturer of HCQ (Srinivasa 2017) and are best managed by taking the drug with food or a glass of milk (Appendix 5). A transient rash, most commonly morbilliform or psoriasiform, can develop in 10% of participants, often with a sustained loading dose, and is often managed by lowering the dose. To avoid this potential side effect, this protocol is using a short loading dose, not a sustained one. Uncommonly, idiosyncratic leukopenia/thrombocytopenia can occur and the drug should not be given to those with underlying bone marrow disorders. Lastly, hypoglycemia can occur and those taking insulin or glucose-lowering drugs are at risk; blood glucose should be monitored.

The safety of HCQ for treatment of patients with COVID-19 disease is unknown. COVID-19 may be associated with cardiac effects. HCQ may prolong QT, resulting in arrhythmias. Participants will be monitored for QT prolongation and counseled about this risk.

Long-term manifestations of HCQ, including retinitis, renal and hepatic disease, and cardiomyopathy (Appendix 5), are not likely in short-term exposure.

7.2.2. *Risks Associated with Azithromycin*

The most common adverse reactions to azithromycin are diarrhea, nausea, abdominal pain, or vomiting (Zithromax USPI, Appendix 6). Severe side effects include serious allergic reactions, including, but not limited to, anaphylaxis, angioedema, and dermatologic reactions such as Stevens-Johnson syndrome. Abnormal liver function, hepatitis, cholestatic jaundice, hepatic necrosis, and hepatic failure have been reported, some of which have resulted in death. Azithromycin can cause abnormal changes in the cardiac electrophysiology that may lead to a potentially fatal irregular heart rhythm. It may increase the risk of death, especially in those with heart problems, compared with those on other antibiotics such as amoxicillin or no antibiotic. The FDA warning indicated that people with pre-existing conditions are at particular risk, such as those with QT interval prolongation, proarrhythmic conditions, low blood levels of potassium or magnesium, a slower than normal heart rate, or those who use certain drugs to treat abnormal heart rhythms. Elderly patients may be more susceptible to development of torsades de pointes arrhythmias.

7.2.3. *QT Risks Associated with Coadministration of HCQ and Azithromycin*

Combination treatment with HCQ + azithromycin was associated with heart-rate corrected QT interval (QTc) prolongation in a study of 84 patients with SARS-CoV-2 (Chorin 2020). Maximal QTc prolongation was observed between Days 3 and 4 of treatment. QTc increase from baseline

was >40 ms in 30% of the patients and 11% exhibited severely prolonged QTc, defined as a maximum increase to >500 ms. Multivariate analysis showed that the development of acute renal failure rather than baseline QTc was a significant predictor of severe QTc prolongation in these patients.

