
COVID-19: coronavirus disease; EOS: end of study; Flu-PRO: inFLUenza patient-reported outcome; HCQ: hydroxychloroquine; HIPAA: Health Insurance Portability and Accountability Act of 1996; SARS-CoV-2: severe acute respiratory syndrome coronavirus 2; SpO2: oxygen saturation; WHO: World Health Organization.
 
Note: ## 800 mg-200 mg LPV/r twice a day or placebo (ascorbic acid 1 gm) twice a day.
 
Note: # denotes 400 mg-100 mg LPV/r twice a day +placebo (ascorbic acid 500 mg) twice a day
 
^a Screening and Day 1, 2, 4, 9, and 14 evaluations will be conducted through a web-based screening tool, HIPAA-compliant video conference (Telehealth), telephone, or text messaging. Screening (Day 0) and Day 1 evaluations may occur on the same day.
 
^b For patients who are hospitalized on Day 28, the last visit will be ±3 days after discharge. The exit survey may also be conducted before day 28 if a participant terminates early and is willing.
 
^c Last day of study medication will be administered on Day 10 LPV/r, and ascorbic acid.
 
^d Last day of QT monitoring will be Day 11.
 
^e These evaluations will be as needed/requested by study participant.
 
*May be omitted if not standard of care to monitor QTc for regimen
											

3. Introduction

This is a randomized, multi-center, placebo-equivalent (ascorbic acid + folic acid)-controlled, blinded platform trial for the treatment of severe acute respiratory syndrome coronavirus 2 (SARS-CoV-2) infection in high-risk adults not requiring hospital admission. The trial will start with hydroxychloroquine (HCQ) (Intervention A), HCQ + azithromycin (Intervention B), and lopinavir-ritonavir (LPV/r) (Intervention C) as experimental interventions. Additional arms will be added as new agents or combinations are prioritized. In addition, if other agents are found to be effective, HCQ, HCQ + azithromycin, or LPV/r may become the control group against which new interventions are measured. Evaluations include safety and tolerability, SARS-CoV-2 viral shedding, and development of lower respiratory tract infection (LRTI). There will be 4 study arms (Arm 1: HCQ + placebo [folic acid], Arm 2: HCQ + azithromycin, Arm 3: LPV/r and Arm 4: placebo [ascorbic acid +/- folic acid],) enrolled to assess a daily dosing regimen administered for 10 days to prevent LRTI or decrease the time to symptom resolution and decrease viral shedding.

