LPV/R is known to cause GI side effects, specifically nausea, vomiting, abdominal pain, and diarrhea. Since participants will have difficulty obtaining medications for symptomatic relief due to these symptoms during the COVID-19 quarantine period, medications to control these symptoms will be given to each participant. Symptomatic medication will be included in separate medication vials and will clearly labeled for participants. Ondansetron 4 mg tabs (#10) and loperamide 2 mg tabs (#10) will be provided to each participant.

Grade 1 or 2

Participants who develop Grade 1 or 2 toxicity (per Division of Acquired Immunodeficiency Syndrome [DAIDS] AE Grading Table; see: <https://rsc.tech-res.com/docs/default->

source/safety/division-of-aids-(daids)-table-for-grading-the-severity-of-adult-and-pediatric-adverse-events-corrected-v-2-1.pdf) that is considered by the site Investigator to be related to the study medication may continue study treatment at the discretion of the site Investigator with close follow up. If a participant chooses to discontinue study treatment, the site should notify the study protocol team within 7 days. These participants will remain on study, off study treatment, and have all evaluations performed.

Grade 3

- Participants who develop a Grade 3 symptomatic toxicity thought by the site Investigator to be related to study drug should have study product withheld, and the site should consult with the Core Protocol team. The participant should be reevaluated every 2 days until the AE returns to Grade ≤ 2 , at which time study drug may be reintroduced at the discretion of the site Investigator in consultation with the protocol team.
- Participants experiencing Grade 3 toxicity requiring permanent discontinuation of study product should be followed up weekly until resolution of the toxicity. Participants will have premature study treatment discontinuation evaluations performed. These participants will remain on study, off study treatment, and have all evaluations performed per the SoA.

Grade 4

- Participants who develop a Grade 4 symptomatic toxicity will have study product permanently discontinued, and the site should notify the Principal Investigator within 72 hours.

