Gastrointestinal disturbance

Nausea, vomiting, and diarrhea are common known possible side effects of LPV/r. Taking with food may improve tolerability. Participants will be counseled extensively about this risk. Ondansetron 4 mg tabs (#10) as needed for nausea and vomiting and loperamide 2 mg tabs (#10) as needed for diarrhea will be provided to each participant. A small supply will be given to participants for at least 2 days of symptom relief. It is anticipated that if symptoms are not controlled with the available medications, that participants may not be able to tolerate study medication. Loperamide is a well tolerated medication available over the counter. Risks include constipation, abdominal cramps. In rare cases, allergic reaction, fatigue/drowsiness, or toxic megacolon may occur. Up to 16 mg can be used per day. With higher than recommended doses, there is risk of QT prolongation. Participants will be instructed not to take more than 4 tablets (8 mg) of loperamide per day. Those participants who take more than the recommended dosage to control diarrhea will have study medication held to reduce the risk of QT prolongation.

Ondansetron may be associated with headache, fatigue, and malaise. Constipation may also occur. Allergic reaction/hypersensitivity may also occur. Participants will be instructed not to take more than 12 mg per day of ondansetron. Those participants who take more than the recommended dose to control symptoms will have study medication held to reduce the risk of QT prolongation.

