- Complete Daily Survey (online, telephone, or text messaging). This Survey will include confirmation of adherence to study therapy dosing and daily swab collection, concomitant medication review, AEs, and symptoms review and objective measures including SpO₂, respiratory rate, temperature, pulse, and ECG. ECG measurements may be recorded on Days 2 through 11 only*. In addition, the modified Flu-PRO survey will be completed.
- *If in DBS sub-study, collect DBS samples for analysis of HCQ, azithromycin, or LPV/r concentrations at any time during this period (1 to 5 times) after study drug dosing has commenced.*
- **EKG monitoring may not be necessary if HCQ/AZ are not used.*

A study team member will be available via Telehealth, text messaging, or telephone to provide support for completion of study procedures. The courier will collect the swabs at minimum within 1 or 2 days of Day 7 and Day 13 and potentially as frequently as daily.

9.3. Days 2 (± 1 day), and Days 4, 9, and 14 (± 2 days)

Contact with study clinician or staff will be conducted via telemedicine (Telehealth) or telephone. Participants will be clinically assessed for signs and symptoms of respiratory distress and will have in person assessment of AEs. As needed, additional contact with the study clinician or staff will be conducted at the request of the participant (e.g., if developing concerning symptoms or an adverse event) or if needed to clarify study procedures or follow-up symptoms.

9.4. Days 14 and 21

The participant will do the following on Days 14 and 21:

- Collect mid-nasal swab for PCR
- Complete Daily Survey (online, telephone, or text messaging). This survey will include confirmation of adherence to study therapy dosing and daily swab collection, concomitant medication review, AEs, and symptoms review and objective measures including SpO₂, temperature, and pulse. In addition, the modified Flu-PRO and WHO Ordinal Scale for Clinical Improvement surveys will be completed.

The courier will collect the swabs of Day 14 and Day 21 with the Day 28 swabs.

9.5. Day 28

The participant will do the following on Day 28:

- Collect mid-nasal swab for PCR

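### Section 7.1 caps ondansetron at 8 tablets (32 mg) per 24 hours, but its own 8-hour interval and the 12 mg limit in Section 7.4 both give 3 tablets

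*Protocol*

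**What the plan says.** Protocol Section 7.1 lists ondansetron as a 4 mg tablet for symptomatic relief. Its dosing cell reads: "Take 1 tablet as needed for nausea every 8 hours. Do not exceed 8 pills per 24 hour period".

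Section 7.4 covers the same drug in its text on gastrointestinal effects of lopinavir-ritonavir (LPV/r):

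- Daily limit: "Participants will be instructed not to take more than 12 mg per day of ondansetron".
- Consequence of going over: "Those participants who take more than the recommended dose to control symptoms will have study medication held to reduce the risk of QT prolongation".
- Supply: "Ondansetron 4 mg tabs (#10) and loperamide 2 mg tabs (#10) will be provided to each participant".
- Purpose of the supply: "A small supply will be given to participants for at least 2 days of symptom relief".

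On QT monitoring in the LPV/r part of the trial, a footnote to the Schedule of Activities (Section 2) says "May be omitted if not standard of care to monitor QTc for regimen", and Section 9.2 adds "EKG monitoring may not be necessary if HCQ/AZ are not used". The SAP covers only the hydroxychloroquine (HCQ) arms and their control, and says nothing about ondansetron.

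**The concern.** The protocol gives two daily maxima for one drug, 32 mg in the dosing table and 12 mg in the toxicity section, and the table's figure does not fit the dosing interval printed just before it.

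The number matters because the protocol itself treats the ondansetron limit as protection against QT prolongation:

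- Section 7.2.4 reports QT prolongation with LPV/r at high doses and when it is given with other QT-prolonging drugs.
- Section 7.3.1 expects nausea and vomiting from the doubled Day 1 dose, so demand for an antiemetic is likely when LPV/r dosing is at its highest.
- Ondansetron is taken at home, as needed and unsupervised.
- Section 7.4 specifies a portable ECG monitor for HCQ and for azithromycin. For LPV/r it specifies only counselling on QT risk.

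A cell of dosing instructions addressed to the participant is a natural source for labels. If labels were written from it, they would carry a ceiling well above the level at which Section 7.4 intends study drug to be held. The hold rule also refers to the recommended dose without naming 12 mg, so a site that reads the table could apply a different threshold.

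**Working it through.** **Inputs**

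- Tablet strength 4 mg, interval 8 hours, cap 8 tablets per 24 hours: Section 7.1.
- Daily limit 12 mg, supply 10 tablets, intended duration at least 2 days: Section 7.4.

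**The plan's figure.** 8 tablets × 4 mg = 32 mg per 24 hours. Reaching it requires one tablet every 24/8 = 3 hours. No other statement in the documents yields 8 tablets or 32 mg.

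**Check 1: the cell's own interval.** Tablets per 24 hours = 24 h / 8 h = 3. Dose = 3 × 4 mg = 12 mg.

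**Check 2: the Section 7.4 limit.** Tablets allowed = 12 mg / 4 mg = 3.

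The two checks use different inputs and give the same answer. Ratio of the printed cap to the limit: 32/12 = 2.67.

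**Check 3: the supply.** Days of supply = 10 / tablets per day.

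| Tablets per day | mg per day | Days from 10 tablets | At least 2 days? |
|---|---|---|---|
| 3 | 12 | 10/3 = 3.33 | yes |
| 5 | 20 | 10/5 = 2.0 | yes, just |
| 8 | 32 | 10/8 = 1.25 | no |

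The supply is at odds with daily use at 8 tablets, but by itself it only bounds intake at 10/2 = 5 tablets a day. It is consistent with 3 and does not fix it. Total drug supplied is 10 × 4 mg = 40 mg.

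**Range on which the two maxima disagree.** More than 12 mg and no more than 32 mg means 4 to 8 tablets, that is 4 × 4 = 16 mg to 8 × 4 = 32 mg in a day.

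**Control comparison.** The neighbouring loperamide cell caps intake at 4 tablets of 2 mg, or 8 mg. Section 7.4 gives the same 4 tablets (8 mg), and 10 tablets last 10/4 = 2.5 days. The same checks therefore pass for loperamide and fail only for ondansetron. The table's broken layout does not explain the mismatch, because the nausea indication, the interval and the cap stand together in one cell.

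**The case against.** The strongest reply is that the cell sets two bounds that can both be obeyed: one tablet every 8 hours, and no more than 8 in 24 hours. The tighter one binds at 3 tablets, so the figure of 8 is slack and 4 to 8 tablets a day is never permitted by the cell as a whole. Section 7.4 also states what participants will be told, and it is 12 mg. For harm to follow, staff would have to overlook that sentence. Further protection comes from the 40 mg total supply, the daily survey of concomitant medication, staff contacts on Days 2, 4, 9 and 14, and exclusion criteria 16 and 19 (long QT history and drugs with known torsades risk). The hold rule follows directly after the 12 mg sentence, so its intended threshold is fairly clear.

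Much of this stands. Intake of 4 to 8 tablets does break the 8-hour interval, the exposure route is conditional, and the supply argument is weaker than the other two. None of it supports 8 as the cap. A daily maximum for an as-needed drug is there for the participant whose nausea persists and who takes tablets sooner than scheduled. A cap 2.67 times what the schedule allows gives that participant no protection, and it contradicts the limit set elsewhere for QT safety.

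**Conclusion.** The concern holds. The ondansetron cap in Section 7.1 is wrong as written: 8 tablets (32 mg) where the cell's own interval and the Section 7.4 limit each give exactly 3 tablets (12 mg), a 2.67-fold difference. It should be fixed because it is a dosing ceiling on a drug whose limit the protocol uses to manage QT risk, in a regimen for which QT monitoring may be omitted.

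The conclusion assumes that the 12 mg in Section 7.4 is the intended limit, which the 8-hour interval supports. Whether any participant was shown the figure of 8 cannot be determined, since the label and instruction sheet are not in the documents. The most any participant could take from the study supply is 40 mg in total. Endpoints, power, sample size and analysis are unaffected.

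**What to change.** - In the Section 7.1 table, replace the ondansetron cap with a maximum of 3 tablets (12 mg) per 24 hours, subject to clinician confirmation.
- In the ondansetron hold rule in Section 7.4, name 12 mg (3 tablets) per day in place of the reference to a recommended dose. This is a clarification, and it removes any doubt about which ceiling triggers the hold.
- Check that the medication label and participant instructions carry the same figure.

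The cost is one number, one phrase and a label check. Nothing in the design or analysis changes.

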7.2.4. Risks Associated with LPV/r

The safety and tolerability of LPV/r has been well characterized through clinical trials and postmarketing experience since first authorization for use in 2001 for the approved HIV indication with over 7 million patient years of exposure. The LPV/r prescribing information ([Appendix 7](#)) describes the known safety profile of LPV/r. Based on clinical trials and postmarketing experience, the most frequently reported adverse drug reactions among patients receiving LPV/r alone or in combination with other antiretroviral agents were gastrointestinal disorders (including diarrhea, nausea, vomiting, and upper and lower abdominal pain), fatigue/asthenia, respiratory tract infection (upper and lower), lipid elevations (hypercholesterolemia and hypertriglyceridemia), musculoskeletal pain (including arthralgia and back pain), and headache (including migraine). Key safety concerns include metabolic abnormalities such as dyslipidemia and insulin resistance, pancreatitis, hepatotoxicity and toxicity in preterm neonates of LPV/r oral solution. In addition, in the HIV population, immune reconstitution inflammatory syndrome manifesting as autoimmune disorders (such as Grave's disease) has been reported. Important potential risks include PR prolongation at therapeutic dosing, and QT prolongation with suprathreshold doses. LPV/r interacts with several drugs since it is an inhibitor of the P450 isoform CYP3A and is likely to increase the plasma concentration of drugs that are metabolized by CYP3A4. Therefore, LPV/r should not be coadministered with drugs primarily metabolized by CYP3A and for which elevated plasma concentrations are associated with serious and/or life-threatening events. A list of such products is included in the LPV/r label. Rare reports of second- or third-degree atrioventricular block in patients with underlying structural heart disease and pre-existing conduction system abnormalities, or in patients receiving drugs known to prolong the PR interval such as verapamil, have been reported in patients receiving LPV/r. LPV/r should be used with caution in such patients. In addition, QT prolongation with suprathreshold doses and when LPV/r is coadministered with drugs known to prolong the QT interval has been reported. Because LPV/r is principally metabolized by the liver, caution should be exercised when administering this drug to patients with impaired hepatic function. Extra monitoring is recommended when diarrhea occurs. The relatively high frequency of diarrhea during treatment with LPV/r may compromise the absorption and efficacy (due to decreased compliance) of LPV/r or other concurrent drugs. Serious persistent vomiting and/or diarrhea with LPV/r use might also compromise renal function. The safety of LPV/r for treatment of patients with COVID-19 disease is unknown. COVID-19 may be associated with cardiac effects. LPV/r may prolong QT at suprathreshold doses and prolong PR at therapeutic doses, resulting in arrhythmias.

7.2.5. Risks Associated with COVID-19 Diagnosis

Enrollment in this protocol will not impact the public health department's advice for self-quarantine. Enrollment may improve morale during quarantine for COVID-19 infection.

COVID-19 infection may be associated with anxiety, and the ability to monitor for disease progression and interact with study clinicians may allay anxiety.

7.3. *Strategies to Minimize Risk*

7.3.1. *Dose Selection*

The recommended dose of HCQ for chronic use in lupus erythematosus is 200 to 400 mg daily, a dose that is safely taken for years including among elderly patients (≥ 65 years). The selection of the time-limited dosing for this study is likely to be safe with transient adverse events (AEs) (gastrointestinal symptoms and rashes) that are self-remitting.

The recommended dose of azithromycin is 500 mg as a single dose on Day 1, followed by 250 mg once daily on Days 2 through 5. This dose has been safely used for several years for treatment of a wide variety of bacterial infections, including pneumonia.

The recommended dose of LPV/r is 400 mg-100 mg twice daily, a dose that has been utilized for several years for treatment of HIV infection as part of combination antiretroviral therapy. To rapidly obtain steady state in this trial, the medication will be dosed at a higher amount (double) on the first day of administration. The loading dose may be associated with GI side effects (nausea, vomiting, and diarrhea).

7.3.2. *Management of Participants to Limit Risks of SARS-CoV-2 Transmission*

To limit the transmission of SARS-CoV-2, participants will receive visits via secure Telehealth in order to limit the movement of persons with potential SARS-CoV-2 and leave clinical space free for ill patients requiring care. Also, to limit exposure in waiting rooms and pharmacies, clinical specimens will be self-collected and medications will be delivered to homes. This will also eliminate exposure of study personnel to SARS-CoV-2.

7.4. *Dose Modification and Toxicity Management*

If a study therapy dose is missed, it should be taken as soon as possible. If it is less than 4 hours before the next dose, the dose should be skipped.

Modification for toxicities is discussed below. Only toxicities related to study medications provided through the study will be considered in the toxicity management section.

LPV/R is known to cause GI side effects, specifically nausea, vomiting, abdominal pain, and diarrhea. Since participants will have difficulty obtaining medications for symptomatic relief due to these symptoms during the COVID-19 quarantine period, medications to control these symptoms will be given to each participant. Symptomatic medication will be included in separate medication vials and will clearly labeled for participants. Ondansetron 4 mg tabs (#10) and loperamide 2 mg tabs (#10) will be provided to each participant.

Grade 1 or 2

Participants who develop Grade 1 or 2 toxicity (per Division of Acquired Immunodeficiency Syndrome [DAIDS] AE Grading Table; see: <https://rsc.tech-res.com/docs/default->

source/safety/division-of-aids-(daids)-table-for-grading-the-severity-of-adult-and-pediatric-adverse-events-corrected-v-2-1.pdf) that is considered by the site Investigator to be related to the study medication may continue study treatment at the discretion of the site Investigator with close follow up. If a participant chooses to discontinue study treatment, the site should notify the study protocol team within 7 days. These participants will remain on study, off study treatment, and have all evaluations performed.

Grade 3

- Participants who develop a Grade 3 symptomatic toxicity thought by the site Investigator to be related to study drug should have study product withheld, and the site should consult with the Core Protocol team. The participant should be reevaluated every 2 days until the AE returns to Grade ≤ 2 , at which time study drug may be reintroduced at the discretion of the site Investigator in consultation with the protocol team.
- Participants experiencing Grade 3 toxicity requiring permanent discontinuation of study product should be followed up weekly until resolution of the toxicity. Participants will have premature study treatment discontinuation evaluations performed. These participants will remain on study, off study treatment, and have all evaluations performed per the SoA.

Grade 4

- Participants who develop a Grade 4 symptomatic toxicity will have study product permanently discontinued, and the site should notify the Principal Investigator within 72 hours.
- Participants experiencing Grade 4 toxicity requiring permanent discontinuation of study product should be followed up weekly until resolution of the AE or return to baseline. These participants will remain on study, off study treatment, and have all evaluations performed per the SoA.

Specific Management of Toxicities Related to Study-provided Drugs

HCQ

Gastrointestinal disturbance

Gastrointestinal disturbance (nausea, vomiting, dyspepsia, abdominal cramps, and diarrhea) is a common known possible side effect of HCQ. Taking with food or milk may improve tolerability.

Visual disturbances

Suspected visual changes should be evaluated for possible etiologies—if an HCQ-associated visual disturbance is suspected, HCQ should be stopped.

Allergic reactions

HCQ should be discontinued permanently if a serious allergic reaction is suspected. These participants will remain on study, off study treatment, and have all evaluations performed per the standard operating procedure(s).

QT prolongation

HCQ is associated with QT prolongation. QT will be assessed during the study using a portable monitor that can transmit electrocardiograms (ECGs) to measure the QTc to a central location, which will be monitored. Participants will be counseled about this risk.

Hypoglycemia

HCQ can be associated with hypoglycemia, particularly among patients with diabetes mellitus who are also taking insulin or sulfonylureas. Participants will be counseled about this risk.

Azithromycin

Gastrointestinal disturbance

Gastrointestinal adverse reactions (nausea, vomiting, abdominal pain, and diarrhea) are common side effect of azithromycin. Most gastrointestinal side effects do not require treatment discontinuation and participants may receive treatment for symptoms (e.g., antiemetics).

Allergic reaction

Serious allergic reactions, including, but not limited to anaphylaxis, angioedema, and dermatologic reactions such as Stevens-Johnson syndrome have been reported with azithromycin treatment. Azithromycin should be discontinued immediately in the event of a hypersensitivity reaction.

QT prolongation

Azithromycin is associated with QT prolongation. QT will be assessed during the study using a portable monitor that can transmit ECGs to measure the QTc to a central location, which will be monitored. Participants will be counseled about this risk.

LPV/r

QT prolongation

LPV/r may be associated with QT prolongation. Participants will be counseled about this risk.

Gastrointestinal disturbance

Nausea, vomiting, and diarrhea are common known possible side effects of LPV/r. Taking with food may improve tolerability. Participants will be counseled extensively about this risk. Ondansetron 4 mg tabs (#10) as needed for nausea and vomiting and loperamide 2 mg tabs (#10) as needed for diarrhea will be provided to each participant. A small supply will be given to participants for at least 2 days of symptom relief. It is anticipated that if symptoms are not controlled with the available medications, that participants may not be able to tolerate study medication. Loperamide is a well tolerated medication available over the counter. Risks include constipation, abdominal cramps. In rare cases, allergic reaction, fatigue/drowsiness, or toxic megacolon may occur. Up to 16 mg can be used per day. With higher than recommended doses, there is risk of QT prolongation. Participants will be instructed not to take more than 4 tablets (8 mg) of loperamide per day. Those participants who take more than the recommended dosage to control diarrhea will have study medication held to reduce the risk of QT prolongation.

Ondansetron may be associated with headache, fatigue, and malaise. Constipation may also occur. Allergic reaction/hypersensitivity may also occur. Participants will be instructed not to take more than 12 mg per day of ondansetron. Those participants who take more than the recommended dose to control symptoms will have study medication held to reduce the risk of QT prolongation.

